#### 13.1.3.2 PK Parameters

Descriptive statistics (N, arithmetic mean, SD, median, minimum, maximum and percent coefficient of variation [%CV]) will be used to summarize the plasma and urine PK parameters for TAK-653, Description (fasted vs fed) and dose level. In addition, geometric mean and CV will be computed for Cmax and AUCs.

Dose proportionality will be tested for TAK-653  $C_{max}$  and AUCs using a power model. For the SRD part, data from the SRD fed Cohort will not be included in the power model. For the SRD/MRD cohorts, the power model will be run after multiple dosing only. The power fit will be assumed as described by the following equation:

[figure not shown]
$$ln(PKParameter) = \beta_0 + \beta_1 ln(Dose) + \varepsilon$$

where  $\beta_0$  is the intercept and  $\beta_1$  is the slope. The dose proportionality would be declared when the

90% CI for  $\beta_1$  lies entirely within the critical region  $1 + \frac{\ln(0.80)}{\ln(r)}$ ,  $1 + \frac{\ln(1.25)}{\ln(r)}$ , where r is the ratio of the highest and the lowest dose in this study. This criterion implies that the 90% CI for the ratio of the central values of PK parameter of interest from the highest dose to the lowest dose is contained completely within the bioequivalence range of (0.80, 1.25). Plots of  $\ln(AUC)$  or  $\ln(C_{max})$  vs  $\ln(Dose)$  may also be used to illustrate dose proportionality or lack of it.

A more detailed analysis will be presented in the SAP.

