4.3 Exploratory/ Additional Objectives

4.4 Study Design

This first-in-human, double-blind, placebo-controlled, combined single-rising dose (SRD)/multiple-rising dose (MRD) phase 1 study in healthy subjects is designed to assess the safety, tolerability, and PK of TAK-653. Approximately 112 healthy male and female volunteers will be enrolled.

This study consists of 2 parts: (1) single ascending doses in 5 cohorts (SRD) and (2) single and multiple ascending doses in 4 cohorts (SRD/MRD). Each cohort will consist of 8 subjects (6 active:2 placebo). Subjects will fast for at least 10 hours before dosing. Cohorts may be added or removed. The decision to dose will be based on emerging safety, PK, and PD data.

Follow-up assessments will occur approximately 14 days after the last dose of study drug to inquire about any ongoing adverse events (AEs) or serious adverse events (SAEs), worsening of AEs or SAEs, or development of new AEs or SAEs, and concomitant medications taken since

| TAK-653-1001 | Page 8 of 32 |
|---------------------------------|----------------|
| Statistical Analysis Plan Final | 22 August 2017 |

final dose. Follow-up will occur by telephone unless abnormal, clinically significant findings are observed upon discharge or at the investigator's discretion. Subjects should then be brought back to the clinic for re-evaluation.

| CCI | | |
|-----|--|--|
| | | |
| | | |
| | | |
| | | |

End of trial (study completion date) will be based on the final data collection date for the entire study which is the Follow-up call/visit.

Part 1: SRD

Subjects will be enrolled in SRD Cohorts. Sentinel dosing will be used for each SRD Cohort. The first 2 subjects (1 active: 1 placebo) in each Cohort will receive either TAK-653 or placebo in parallel, followed by a minimum 24-hour gap to ensure adequate evaluation of safety and tolerability prior to administering the same dose of TAK-653 or placebo to the remaining subjects within the Cohort (5 active: 1 placebo). Dosing of the remaining subjects will proceed in a staggered fashion with no more than 3 subjects being dosed at a time and having an approximate 24-hour gap before the next group of subjects is dosed. Each dose cohort will be examined sequentially to ensure adequate evaluation of all available safety, tolerability, PK, and PD data prior to administering the next dose level.

| Pretreatment Period | | Treatment Period | | | | Follow up (d) |

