A single dose of TAK-653 or placebo will be administered on Day 1 followed by approximately 120 hours for safety, tolerability, PK, and PD assessments. Once daily (QD) multiple dosing will begin on Day 6 and continue through Day 18 (13 days). Initiation of the multiple-dose phase on Day 6 may be adjusted based on emerging safety, PK, and/or PD data. Neither sentinels nor staggered dosing are used in the SRD/MRD. Subjects in the SRD/MRD Cohorts will be kept in the study unit for at least 72 hours after the last dose for safety assessments before discharge. The total confinement period planned is 21 days. Cohort 4 as well as any additional cohorts are optional (Note: at the time of this SAP, Cohort 4 has been initiated), to be used if emerging safety and/or PK or PD data warrant further study at a different dose. Follow-up assessments will occur on Day 31 (±2).

Each dose cohort will be examined sequentially to ensure adequate evaluation of all available safety tolerability PK and PD data prior to administering the next dose level

Part 2: SRD/MRD Study Schematic

| Pretreatment Period | | Treatment Period | | | | Follow- up (e) | |
|---------------------|-------------------------------------|---|--|---|---------------------------------|-------------------|----------------|
| Screening | Check-in Baseline Assessments | TAK-653 Single Dose Study Assessments (a) (b) (d) | Safety and PK Assessments (d) | TAK-653 QD dosing Study Assessments (a) (b) (c) (d) | Safety and PK Assessments | Study Exit | |
| Day -28 to -2 | Day -1 | Day 1 | Days 2-5 | Days 6-18 | Days 19-20 | Day 21 | Day 31 (±2) |
| | 4 | | Confin | ement | | • • • • • • • • | |

(a) Study assessments include PK sample collection throughout.

(b) EEG assessments are scheduled on Days 1, 11, 18, and ET.

| (C) | |
|-----|----|
| (d) | CC |

(e) The Follow-up assessments will occur by telephone unless abnormal, clinically significant findings are observed upon discharge. In this case or per investigator's discretion, subjects should return to the clinic for re-evaluation.

| | Planned TAK-653 Dose (a) (b) (c) | | | |
|--------|----------------------------------|--------|-----------|--|
| Cohort | Planned | Actual | Subjects | |
| 1 | X mg | 0.3 mg | 6 TAK-653 | |
| | | | 2 placebo | |
| 2 | X mg | 1.0 mg | 6 TAK-653 | |
| | | | 2 placebo | |
| 3 | X mg | 3.0 mg | 6 TAK-653 | |
| | | | 2 placebo | |
| 4 | X mg | 6.0 mg | 6 TAK-653 | |
| | | | 2 placebo | |
| 5 | X mg | 9.0 mg | 6 TAK-653 | |

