| | | | 2 placebo | |

Part 2: Summary of SRD/MRD Dose Cohorts

(a) Dosing for the first SRD/MRD Cohort will not begin until there is acceptable safety, tolerability, and available PK and PD data at the same or higher dose level after a single dose from at least the first 3 SRD Cohorts. Dose escalation to subsequent Cohorts will be based on review of safety, tolerability, and available PK and PD data from previous Cohorts. The subsequent dose level may be higher, lower, or the same as the preceding dose level.
(b) In each Cohort, a single dose will be administered on Day 1 followed by 120 hours of safety, tolerability, PK, and PD assessments. QD multiple doses will proceed from Day 6 through Day 18.

(c) TAK-653 or placebo tablets will be administered orally to subjects after an overnight fast of at least 10 hours.

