Additionally, box plots of TAK-653 dose-normalized C_{max} and AUCs versus dose will be provided for each part (fasted cohorts only). Box plots of TAK-653 C_{max} and AUCs comparing fasted versus fed cohorts will also be provided.

Dose proportionality will be tested for SRD cohorts (fasted cohorts only) on Day 1 and for SRD/MRD cohorts after multiple dosing on Day 18 for TAK-653 C_{max} and AUCs using a power model. The power fit will be assumed as described by the following equation:

 $\ln(PK \ Parameter) = \beta_0 + \beta_1 \ln(Dose) + \varepsilon$

where β_0 is the intercept and β_1 is the slope. The dose proportionality will be declared when the 90% confidence interval for β_1 lies entirely within the critical region.

$$\left(1 + \frac{\ln(0.80)}{\ln(r)}, 1 + \frac{\ln(1.25)}{\ln(r)}\right)$$

where r is the ratio of the highest and the lowest dose in this study. This criterion implies that the 90% CI for the ratio of the central values of PK parameter of interest from the highest dose to the lowest dose is contained completely within the bioequivalence range of (0.80, 1.25) [2]. Plots of ln(AUC) or ln(C_{max}) vs ln(Dose) may also be used to illustrate dose proportionality or lack of it.

A power model will be performed to test whether the slope=1 in the power model and whether the point estimate of the slope is significantly different from 0 or not.

The effect of food on the PK of TAK-653 will be evaluated via a paired t-test. The point estimates and 90% CIs for the ratio of C_{max} and AUC central values for TAK-653 tablets administered after fed conditions vs those obtained in the fasted state will be determined. The food effect on t_{max} will also be evaluated using a non-parametric Wilcoxon rank sum test.

All attempts will be made to have a distribution of ^{CCI} times within the prescribed window of 2 to 6 hours postdose on Day 12 for SRD/MRD Cohort 3; for example, the ^{CCI} may be collected at 2 hours postdose from the first subject, 3 hours postdose from the

| TAK-653-1001 | Page 22 of 32 |
|---------------------------------|----------------|
| Statistical Analysis Plan Final | 22 August 2017 |
| | |

second subject, 4 hours postdose from the third subject, and 6 hours postdose from the fourth subject with a collection window of +1 hour for each subject.

| The CCI | , if available, will be presented |
|--|---------------------------------------|
| in a data listing. The ratio of TAK-653 ^{COI} | on Day 12 to the TAK-653 plasma |

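### The single-dose dose-proportionality model leaves out the fasted Day 1 profiles from Part 2 without a stated reason, so the slope's 90% CI is about 31% wider than the collected data allow

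*Protocol*

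**What the plan says.** Protocol 13.1.3.2 tests dose proportionality of TAK-653 Cmax and AUCs with a power model. Fed data are excluded in Part 1. For Part 2 it states: "For the SRD/MRD cohorts, the power model will be run after multiple dosing only". SAP 7.7.2 puts it this way: "Dose proportionality will be tested for SRD cohorts (fasted cohorts only) on Day 1 and for SRD/MRD cohorts after multiple dosing on Day 18". Part 2 Day 1 is in neither list, and neither document gives a reason.

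The decision rule in SAP 7.7.2 is: "The dose proportionality will be declared when the 90% confidence interval for β_1 lies entirely within the critical region". The limits are 1 + ln(0.80)/ln(r) and 1 + ln(1.25)/ln(r), "where r is the ratio of the highest and the lowest dose in this study".

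The design in SAP 4.4 gives Part 2 a single-dose phase: "In each Cohort, a single dose will be administered on Day 1 followed by 120 hours of safety, tolerability, PK, and PD assessments". Dosing follows a fast of at least 10 hours. Protocol Table 9.c and SAP 7.7.1 give Part 2 Day 1 the same plasma sampling times as Part 1 up to 120 hours. Protocol 5.4.2 and SAP 5.2 list Day 1 Cmax, AUClast and AUC-infinity as secondary endpoints for all cohorts.

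**The concern.** The secondary objective covers the PK of single as well as multiple doses. A Part 2 Day 1 profile measures the same thing as a fasted Part 1 profile: exposure after one fasted dose. On the SAP's table it also brings in 6 mg, a dose that Part 1 does not study. Leaving these profiles out of the slope estimate gives up precision that has already been paid for in subjects and samples.

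At stake is how informative the single-dose slope is, and how often the prespecified yes/no rule can say yes when exposure really is proportional. Protocol 4.3 already describes the PK as linear on preliminary data. A formal test that fails only because its interval is wide would sit awkwardly beside that statement.

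**Working it through.** Neither document states a power, a CV or a sample size for this test, so there is no planned figure to reproduce.

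**Inputs**
- Part 1 (SAP 4.4 table): 0.3, 1, 3, 5, 9 and 18 mg, 6 active each: 6 × 6 = 36 fasted profiles.
- Part 2 (SAP 4.4 table): 0.3, 1, 3, 6 and 9 mg, 6 active each: 5 × 6 = 30 Day 1 profiles.
- Share omitted: 30 of 66. On the 5 + 4 cohorts planned in the Protocol it is 24 of 30 + 24 = 54.
- r = 18/0.3 = 60. Margin m = ln(1.25)/ln(60) = 0.2231/4.0943 = 0.0545, so the limits are 0.9455 to 1.0545.

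**Precision.** For ordinary least squares of ln(PK) on ln(dose), SE(slope) = σ/√Sxx, where Sxx is the sum of squared deviations of ln(dose), taken within part when a Part term is fitted.
- SRD only: Sxx = 67.12, 34 df, t(0.95) = 1.691.
- Pooled with Part term: Sxx = 67.12 + 46.07 = 113.19, 66 − 3 = 63 df, t(0.95) = 1.669.
- SE ratio, pooled to SRD only: √(67.12/113.19) = 0.770, a 23% reduction at any σ.
- CI width ratio, SRD only to pooled: (1.691/8.193)/(1.669/10.639) = 1.31.

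**Chance of declaring proportionality.** Assumptions: log-normal data, true slope exactly 1, σ = √ln(1 + CV²), and the same σ in both parts and at all doses. The probability that the whole 90% CI lies within 1 ± 0.0545 was obtained by integrating over the residual variance.

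| Assumed CV | Half-width, SRD only | Half-width, pooled | Declared, SRD only | Declared, pooled |
|---|---|---|---|---|
| 15% | 0.031 | 0.023 | 80% | 97% |
| 20% | 0.041 | 0.031 | 43% | 79% |
| 25% | 0.051 | 0.039 | 13% | 51% |
| 30% | 0.061 | 0.046 | 2% | 24% |
| 32% | 0.064 | 0.049 | 1% | 16% |
| 38% | 0.076 | 0.058 | under 0.1% | 2% |

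**Which CV?** The documents report none. The only spread is in Protocol 6.2.2, for 1 mg on Day 18: Cmax mean 24.9 (range 14.7 to 34.9) ng/mL and AUC24 mean 503 (range 256 to 741) h*ng/mL. Assuming six active subjects and an expected range of 2.534 SD:
- Cmax: (34.9 − 14.7)/2.534/24.9 = 0.32.
- AUC24: (741 − 256)/2.534/503 = 0.38.
- On the log scale, ln(34.9/14.7)/2.534 = 0.341 (CV about 35%) and ln(741/256)/2.534 = 0.419 (CV about 44%).

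A range from six subjects is a weak guide. For Cmax it is compatible with a log SD of roughly 0.21 to 0.69 (5% to 95%). It also comes from one dose after multiple dosing, not from single-dose data.

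**The case against.** The strongest reply is that analysing by part is a reasonable choice and that little depends on it. PK summaries and plots are organised by part. The parts differ: Protocol 7.4 allows food about 2 hours after dosing in Part 2 but continues the fast for 4 hours in Part 1, and sampling ends at 120 hours against 144 or 168. A Part term removes only a constant shift, not an effect of truncated sampling that changes with dose. The objective is to determine the PK, not to prove proportionality; the study was not sized on power; and escalation rests on predicted exposure, not on this test.

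Much of this stands, and it is why the severity is low. The meal and sampling differences argue for a Part term, for leaving AUClast out of the pooled fit and for keeping the SRD-only fit. They do not explain omitting Cmax and the comparable AUCs altogether.

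A reader might also infer that the Part 2 Day 1 profiles are thrown away. The documents do not support that. SAP 7.7.2 summarises the parameters by dose level and Day, lists them, and plans dose plots for each part. The profiles are missing from one model only. The Protocol wording does exclude them from it; the SAP simply does not list them.

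**Conclusion.** The point holds as a missed gain in efficiency. Omitting 30 of 66 profiles makes the single-dose slope CI about 31% wider than it need be. That figure depends on the SAP's cohort tables and on equal variance across parts, but not on the CV.

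A reader might go further and conclude that the omission is what puts the criterion out of reach. The numbers do not support that. At the CVs suggested by the Day 18 ranges, the pooled fit would still declare proportionality only about 16% of the time for Cmax (32%) and 2% for AUC (38%). The log-scale estimates are less favourable still. In that region the main causes are the 0.80 to 1.25 criterion at r = 60, the variability and six active subjects per dose. Pooling changes the outcome materially at a CV of about 20% to 30%. Since the CV is an assumption, the size of the gain in declaration probability is uncertain; the gain in precision is not. Failing to declare proportionality would not itself show non-proportionality. No error or contradiction between the documents is claimed.

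**What to change.** In Protocol 13.1.3.2 and SAP 7.7.2, run the Day 1 power model on all fasted Day 1 profiles, SRD plus SRD/MRD, with a fixed term for Part. Do this for Cmax, AUC-infinity and AUC24. Leave AUClast out of the pooled fit because the last sampling time differs between parts. Report the SRD-only fit as a sensitivity analysis, and keep the Day 18 model unchanged. If the SRD-only model is preferred as the main one, state the reason.

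The cost is a few lines of SAP text and one extra model per parameter, with no new data. The small downside is residual non-comparability from meal timing and sampling length, to the extent that it varies with dose; comparing the pooled and SRD-only slopes would help show it.

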#### 13.1.4 Pharmacodynamic Analysis

## 13.1.5 Safety Analysis

All safety data will be presented in listings. Where applicable, within each part, safety data will be summarized by placebo, each TAK-653 dose level, TAK-653 overall, and overall total. Placebo data will be pooled across cohorts within each part. These summaries will not contain data from the fed portion. Data from the food effect cohort will be summarized separately by placebo fed, placebo fasted, TAK-653 fed, and TAK-653 fasted.

#### 13.1.6 AEs

All AEs will be coded by system organ class (SOC) and preferred term (PT) using MedDRA. TEAEs with onset occurring within 30 days (onset date − last date of dose +1≤30) after study drug administration will be listed, and included in the summary tables. TEAEs will be summarized by SOC and PT. The following summary tables will be included in the report: summary of TEAEs and drug-related AEs, relationship of AEs to study drug (related vs not-related), severity of AEs and related AEs. AEs leading to study drug discontinuation and SAEs will be listed. Data listings will be provided for all AEs including PTE, TEAEs, AEs leading to study drug discontinuation, and SAEs.

#### 13.1.6.1 Clinical Laboratory Evaluation

Individual results of laboratory tests from hematology, chemistry, and urinalysis that meet Takeda's markedly abnormal value (MAV) criteria to be defined in the SAP will be listed and summarized. Baseline, postdose, and change from Baseline to postdose laboratory data will be summarized. All clinical laboratory data will be listed.

## 13.1.6.2 Vital Signs

Individual results of vital signs that meet Takeda's MAV criteria to be defined in the SAP will be listed and summarized. Observed values and changes from Baseline in vital sign measurements (systolic and diastolic blood pressure, heart and respiratory rate, and oral temperature) will be summarized. All vital signs data will be provided in the data listings.

#### 13.1.6.3 ECGs

Individual results of ECG parameters that meet Takeda's MAV criteria to be defined in the SAP will be listed and summarized. Observed values and changes from Baseline in ECG parameters will be summarized. All vital signs data will be provided in the data listings.

Shift tables will be generated for the investigator's ECG interpretations by above group. All ECG data will be provided in the data listings.

## 13.1.6.4 Safety EEGs

All screening and postdose safety EEG assessments will be listed. A shift table will summarize the number of subjects who changed status from Baseline.

## 13.2 Interim Analysis and Criteria for Early Termination

No interim analysis is planned.

## 13.3 Determination of Sample Size

The sample size chosen of 8 subjects in each Cohort (6 active: 2 placebo) is considered to be sufficient for evaluation of safety, tolerability, and PK of each cohort. The sample size was not based on statistical power considerations.

## 14.0 QUALITY CONTROL AND QUALITY ASSURANCE

## 14.1 Study-Site Monitoring Visits

Monitoring visits to the study site will be made periodically during the study to ensure that all aspects of the protocol are followed. Source documents will be reviewed for verification of data recorded on the eCRFs. Source documents are defined as original documents, data, and records. The investigator and institution guarantee access to source documents by the sponsor or its designee (CRO) and by the IEC.

All aspects of the study and its documentation will be subject to review by the sponsor or designee (as long as blinding is not jeopardized), including but not limited to the Investigator's Binder, study drug, subject medical records, informed consent documentation, documentation of subject authorization to use personal health information (if separate from the informed consent forms), and review of eCRFs and associated source documents. It is important that the investigator and other study personnel are available during the monitoring visits and that sufficient time is devoted to the process.

#### 14.2 Protocol Deviations

The investigator should not deviate from the protocol, except where necessary to eliminate an immediate hazard to study subjects. Should other unexpected circumstances arise that will require deviation from protocol-specified procedures, the investigator should consult with the sponsor or designee (and IEC, as required) to determine the appropriate course of action. There will be no exemptions (a prospectively approved deviation) from the inclusion or exclusion criteria.

The site should document all protocol deviations in the subject's source documents. In the event of a significant deviation, the site should notify the sponsor or its designee (and IEC, as required). Significant deviations include, but are not limited to, those that involve fraud or misconduct, increase the health risk to the subject, or confound interpretation of primary study assessment. A Protocol Deviation Form should be completed by the site and signed by the sponsor or designee for any significant deviation from the protocol.

Every attempt will be made to collect each PK and/or PD blood sample at the designated time point, and the actual time of each blood sample will be recorded on the source document and eCRF. Table 14.a defines the windows allowed for sample collections.

However, blood samples not collected within the interval specified for the scheduled sample time should be reported to Takeda using the Protocol Deviation Form.

Protocol Deviation Forms are to be completed for PK/PD samples collected outside of the following intervals:

Table 14.a Windows for PK/PD Blood Sample Collection

Minutes	Nominal Sampling Time
no more than 30 minutes predose	0 hour
±5	immediately postdose to ≤6 hours
±10	>6 hours to ≤12 hours postdose
±15	>12 hours to ≤24 hours
±30	>24 hours

## 14.3 Quality Assurance Audits and Regulatory Agency Inspections

The study site also may be subject to quality assurance audits by the sponsor or designees. In this circumstance, the sponsor-designated auditor will contact the site in advance to arrange an auditing visit. The auditor may ask to visit the facilities where laboratory samples are collected, where the medication is stored and prepared, and any other facility used during the study. In addition, there is the possibility that this study may be inspected by regulatory agencies, including those of foreign governments (eg, the FDA, the United Kingdom Medicines and Healthcare products Regulatory Agency [MHRA], the Pharmaceuticals and Medical Devices Agency of Japan). If the study site is contacted for an inspection by a regulatory body, the sponsor should be notified immediately. The investigator and institution guarantee access for quality assurance auditors to all study documents as described in Section 14.1.

